$$Lvl1 : Y_{ij} = \beta_{0i} + \beta_{1i}S_{1j} + \beta_{2i}S_{2j} + e_{ij}$$

Where Y_{ij} is the continuous outcome variable for person i at time j where $i = 1, 2, \dots, N$ and $j = 1, 2, \dots, 6$ (for pre-treatment, session 1, ..., session 5); β_{0i} through β_{2i} values are the random effects; S_{1j} is time at the first stage of the clinical trial (pre-treatment to re-randomization point after session); S_{2j} is time at the second stage of the clinical trial (session 1 to session 5); α_1 specifies the treatment arm contrast comparison after the initial randomization; α_2 specifies the treatment arm contrast comparison after re-randomization; Z_{SES} is a control variable for participant socioeconomic status; and Z_{age} is a control variable for participant age.

Note that for simplicity, the above equations only show one α_2 value. Since our four contrasts are not orthogonal, we will attempt to include all four α_2 contrasts in one `rjags` model for each outcome variable of interest. If this added complexity prevents model convergence, we will run four separate models, each specifying one of the four α_2 contrast codes.

Estimands. We have identified four estimands of interest upon which to interpret our treatment dropout hypotheses: Study arm differences in (1) average likelihood to have dropped out during or before session 5 training (i.e., time-specific outcome of primary interest), (2) average likelihood to have dropped out during or before session 2 training (i.e., time-specific outcome of secondary interest), (3) average likelihood to have dropped out during or before session 3 training (i.e., time-specific outcome of secondary interest); and (4) average likelihood to have dropped out during or before session 4 training (i.e., time-specific outcome of secondary interest).

- [Pre-Registration Table 1.png](#)
- [Pre-Registration Table 2.png](#)
- [Pre-Registration Equation Set 1.png](#)
- [Pre-Registration Table 3.png](#)
- [Pre-Registration Equation Set 2.png](#)

Transformations

As stated above, we will center time (S1) at zero for all longitudinal models such that the pre-intervention assessment points for all participants, regardless of the date of their initial assessment, will be set to 0.

We will mean center any continuous baseline covariates (e.g., SES).

Inference Criteria

We will make statistical inferences according to obtained HPD 95% Credible Intervals.

Data Exclusion

We will exclude participants who completed the DASS-A screener multiple times until they met eligibility criteria. We will also exclude participants who did not complete the first training session and subsequent assessment battery because we could not apply the attrition algorithm to these participants. As such, we are unable to know whether these individuals would have been identified by our algorithm as being at lower or at higher risk for dropping out, and, if they were identified as being at higher risk for dropping out, whether they would have been randomized to receive telecoaching or not. While excluding these participants interferes with being able to make causal claims (i.e., this is not an intent-to-treat sample), it allows for us to reduce uncertainty and error in group assignment. Since we aim to compare outcomes between groups, we have decided to prioritize accurate group assignment over an ITT sample with group classification uncertainty. As such, our primary analyses will be conducted on the 1075 session 1 assessment completers and our secondary completer analyses will be conducted on the participants who completed all five training sessions (whether those sessions were composed of psychoeducation or CBM-I). To be considered a completer within the high-risk plus telecoaching group, those participants must also have engaged with a telecoach at least once.

Missing Data

The present data likely exhibit two missing data patterns. At the item level, participants had the option to select Prefer Not to Answer when completing RR, the BBSIQ, the OASIS, and the DASS-AS, likely resulting in a general missing data pattern when they did so. In such cases, which we expect to be rare, we will analyze the mean of the available items.

At the scale level, we expect attrition to yield a monotone missing data pattern. To find any measured variables that may relate to this pattern of missing data and that are not already included in the analysis models, we will test whether demographics, training confidence, change importance, and device use correlate with binary indicators of scale-level missingness at each time point given that analyses of missingness in prior MindTrails studies have found that these variables predict missingness (e.g., Eberle et al., 2020; Hohensee et al., 2020). Following an inclusive analysis strategy (Collins et al., 2001), we will include any variables that correlate with missingness at greater than $.40$ (which Enders, 2010, p. 133, states is the correlation yielding the “most useful” auxiliary variables) as auxiliary variables in our Bayesian analyses to correct for any systematic bias resulting from these variables’ relationships with missingness.

Exploratory Analysis

No response

Other

References

Beard, C. (2011). Cognitive bias modification for anxiety: current evidence and future directions. *Expert Rev Neurother*, 11(2), 299–311. <https://doi.org/10.1586/ern.10.194>

Clark, D. M., Salkovskis, P. M., Ost, L. G., Breitholtz, E., Koehler, K. A., Westling, B. E., & Gelder, M. (1997). Misinterpretation of body sensations in panic disorder. *Journal of Consulting and Clinical Psychology*, 65, 203-213.

Collins, L. M. (2018). Optimization of behavioral, biobehavioral, and biomedical interventions: The multiphase optimization strategy (MOST). Cham, Switzerland: Springer.

Collins, L. M., Schafer, J. L., & Kam, C-M. (2001). A comparison of inclusive and restrictive strategies in modern missing data procedures. *Psychological Methods*, 6, 330-351.
<https://doi.org/10.1037/1082-989X.6.4.330>

Eberle, J. W., Boukhechba, M. O., Sun, J., Zhang, D., Funk, D. H., Barnes, L. E., & Teachman, B. A. (2020). Shifting episodic prediction with online cognitive bias modification: A randomized controlled trial. Preprint under review. PsyArXiv. <http://doi.org/d54p>

Enders, C. K. (2010). Applied missing data analysis. Guilford press.

Eysenbach G. (2005). The law of attrition. *Journal of medical Internet research*, 7(1), e11.
<https://doi.org/10.2196/jmir.7.1.e11>

Hallion, L. S., & Ruscio, A. M. (2011). A Meta-Analysis of the Effect of Cognitive Bias Modification on Anxiety and Depression. *Psychological Bulletin*.
<https://doi.org/10.1037/a0024355>

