individuals assigned to all arms of the CBM-I treatment, as compared to those randomized to complete a series of psychoeducation tutorials, will show a greater increase in positive interpretation bias and a greater reduction in negative interpretation bias and anxiety symptoms from pre-treatment to post-treatment (where post-treatment is measured immediately following session 5). We also expect that treatment gains will be maintained for individuals assigned to CBM-I (vs. psychoeducation) at two-month follow-up. When comparing outcomes within the three CBM-I arms of the study, we expect the high-risk for attrition plus telecoaching group to show greater increases in positive interpretation bias and greater reductions in negative interpretation bias and anxiety symptoms compared to the high risk for attrition group who were not randomized to receive telecoaching. Comparisons between the low risk for attrition group and the high risk for attrition groups (with or without telecoaching) are of secondary interest and these hypotheses are non-directional.

Treatment Dropout Hypotheses

Online mental health interventions have long-been plagued by high user dropout (Eysenbach, 2005). Therefore, it is important to investigate whether adding minimal human contact (i.e., providing telecoaching) to participants identified as being at high risk for treatment dropout improves retention in this online intervention trial. We expect that CBM-I participants identified as being at high risk of treatment dropout who were randomized to receive a supplemental telecoaching intervention will drop out at a later session than high risk CBM-I participants who did not get randomized to the telecoaching intervention. Further, we expect that the three CBM-I arms of the trial will be associated with less attrition than the psychoeducation comparison group.

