Per protocol, we planned to recruit and enroll 1,000 highly anxious individuals and sequentially employ a series of weighted randomization rules to achieve four treatment arms (i.e., four study conditions) of approximately equal weight (approximately 250 participants per group). Data collection is now complete and we enrolled 1746 participants in total. Of these, 1238 started the first training session and are considered intent to treat (ITT). At Stage 1 randomization, 984 ITT participants were assigned to CBM-I, and 254 ITT participants were assigned to psychoeducation. 1075 ITT participants completed assessments immediately following the first training session (835 in CBM-I and 240 in psychoeducation) and are included in our primary analyses. The 835 CBM-I completers of the session 1 assessments were classified as higher ($n = 547$) or lower ($n = 288$) risk of study dropout, whereas the 149 CBM-I participants who did not complete the session 1 assessments were not able to be classified as higher or lower risk of study dropout. Of the 547 CBM-I participants classified as higher risk of study dropout, at Stage 2 randomization 282 were assigned to receive coaching and 265 were assigned to no change. In total, 559 of the 1238 ITT participants completed five training sessions and are deemed treatment completers.

Sample Size Rationale

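### The completer analysis selects on an outcome and adds a telecoach-engagement condition in one arm only, so Stage 2 randomization no longer protects it; the direction of bias is not identified

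*Combined protocol and SAP*

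**What the plan says.** Analysis Plan, Data Exclusion, sets the primary analysis on the 1075 participants with session 1 assessments and then states that "our secondary completer analyses will be conducted on the participants who completed all five training sessions", whether the sessions were CBM-I or psychoeducation. It continues that, to count as completers in the high-risk telecoaching arm, "those participants must also have engaged with a telecoach at least once". No other arm has a matching condition, and engagement is not defined.

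Two other places define a completer by five sessions alone. Sample Size gives 559 of 1238 as treatment completers with no mention of a telecoach. Models Testing the Probability of Dropping Out of Treatment likewise ties the term to finishing all five sessions.

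Completion is also a tested outcome. The Treatment Dropout Hypotheses predict that high-risk participants given telecoaching "will drop out at a later session than high risk CBM-I participants who did not get randomized to the telecoaching intervention", and also state that "we expect that the three CBM-I arms of the trial will be associated with less attrition than the psychoeducation comparison group". The dropout model's estimand of primary interest is the "average likelihood to have dropped out during or before session 5 training".

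On allocation, Sample Size reports that "at Stage 2 randomization 282 were assigned to receive coaching and 265 were assigned to no change".

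**The concern.** The 547 high-risk participants were re-randomized after the session 1 assessment. Excluding people without that assessment therefore does not disturb the Stage 2 contrast, which is the cleanest comparison in the trial. The completer rule disturbs it twice. It selects on completion, which coaching is predicted to change. It then drops non-engagers from the telecoaching arm, while the comparison arm keeps people who would not have engaged had they been offered a coach.

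The effect reaches beyond one contrast. In Pre-Registration Table 2 the telecoaching arm has a non-zero code in three of the four second-stage contrasts (a2,1, a2,2 and a2,3).

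The plan concedes that its sample is not intent-to-treat, but only for the session 1 exclusion. It gives no caveat, weighting or complier method for the completer set. At stake is whether a completer result can be read as support for the directional telecoaching hypotheses.

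**Working it through.** **Counts in Sample Size.** These reproduce: 984 + 254 = 1238; 835 + 240 = 1075; 547 + 288 = 835; 282 + 265 = 547; 984 − 835 = 149. Completers: 559/1238 = 45.2%, not split by arm.

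**What is not given.** The documents have no completion rate by arm, no engagement rate, and no correlation of either with outcome. Everything below assumes these values and assumes that coaching has no true effect on outcome.

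**One-arm rule, simple bound.** Treat the propensity to engage as standard normal among completers, with a fraction P engaging. The mean propensity of those kept is φ(z)/P, with z the (1 − P) quantile. Multiply by r, the correlation of propensity with outcome.
- P = 0.7: 0.3477/0.7 = 0.497. With r = 0.2 to 0.3 the shift is 0.10 to 0.15 SD.
- P = 0.9: 0.1755/0.9 = 0.195. The shift is 0.04 to 0.06 SD.

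**One-arm rule, latent-trait simulation (4 million draws per setting).** One trait drives improvement (correlation 0.2 or 0.3), completion (0.7) and engagement (0.7). The shifts are smaller, because completion has already narrowed the range of the trait and engagement reflects it only in part.
- 70% of all those assigned engage: +0.03 to +0.05 SD. At 45% completion, 0.383/0.45 = 85% of completers have then engaged.
- 70% of completers engage: +0.05 to +0.08 SD.

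At 70% engaged, the one-arm rule alone therefore spans about +0.03 to +0.15 SD, depending on the model.

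**Selection on completion, same simulation, no engagement rule.** If telecoaching retains people who would otherwise have left, its completer set gains participants with lower values of the trait.

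| Completion, no telecoaching vs telecoaching | Shift, r = 0.2 | Shift, r = 0.3 |
|---|---|---|
| 45% vs 45% | 0.00 | 0.00 |
| 45% vs 50% | −0.01 | −0.02 |
| 45% vs 60% | −0.03 | −0.05 |
| 34% vs 50% | −0.04 | −0.06 |

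**Both together.** With 30% to 90% of those assigned engaging, the net runs from −0.05 to +0.14 SD. Three examples at r = 0.3:
- 45% vs 60% completion, 70% engaged: about 0.00
- 34% vs 50% completion, 70% engaged: −0.01
- 45% vs 50% completion, 50% engaged: +0.07

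**Opposite take-up.** If those doing worse engage more (engagement loading −0.3, r = 0.3, completion 45% vs 50%), the rule itself shifts the result by −0.04 SD at 70% engaged and −0.06 SD at 50%.

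**Precision.** At 45% completion there are 282 × 0.45 ≈ 127 against 265 × 0.45 ≈ 119 completers. If half of the 127 engaged, the comparison is about 63 against 119. Power for d = 0.35 in a simple two-group comparison (two-sided 5% assumed) falls from 78% to 62%. For 282 against 265 with complete data it is about 98%.

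**The case against.** The analysis is labelled secondary, and the primary set keeps everyone re-randomized at Stage 2, so the main telecoaching contrast is as randomized. Requiring receipt of the assigned component is a familiar per-protocol rule, and arms without a coach cannot have a matching condition. All of this stands, and it limits the weight of the point. It does not make the filtered comparison a fair one.

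A reader might go further and infer that the analysis is tilted toward telecoaching and would favour it even if coaching did nothing. The documents do not support that. They do not say who engaged or why: engagement could reflect motivation, scheduling or greater need. The retention effect that the trial predicts pulls against telecoaching among completers.

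Nor should 0.10 to 0.15 SD be read as the expected bias. It assumes that r applies directly between propensity and outcome within five-session completers, and it ignores the opposing selection. Comparing it with d = 0.35 adds little, because Sample Size Rationale used that value for a 2×3 design with a delivery-platform factor that was later not randomized, and says that an effect size could not be determined in advance.

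**Conclusion.** The concern holds as a defect of definition and selection. Two facts come from the text without any assumption: completers are chosen on a post-randomization outcome that the trial tests, and an extra condition applies to one arm only. Stage 2 randomization therefore does not protect the completer comparison of telecoaching with no telecoaching, and the definition disagrees with the two other places that use five sessions alone.

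The sign and size of the bias are not identified. The one-arm rule probably favours telecoaching if engagement marks people who do better, but the illustrative net range crosses zero. A contrast whose bias has unknown sign cannot support a directional hypothesis. The primary analysis is unaffected by this rule. The change is worth making, but it ranks below any problem in the primary analysis.

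**What to change.** 1. Use one completer criterion, five sessions, in all four arms, and reconcile Data Exclusion with Sample Size and the dropout-model section.
2. Label every completer comparison descriptive and non-causal. A common criterion is not enough, because it still selects on completion (up to −0.06 SD in the illustration).
3. Base telecoaching inference on the 282 and 265 as randomized.
4. Report completers and engaged participants by arm, and define engagement.
5. If the effect of coaching received is wanted, replace the one-arm filter with a complier average causal effect in all 547. Use Stage 2 assignment as the instrument and the defined engagement as receipt. State the exclusion restriction (assignment acts on outcome only through engagement) and how missing outcomes are handled.

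Items 1 to 4 need a few sentences and a table. Item 5 needs extra modelling for each of the six outcome scores to which it is applied, and gives a wider interval. In its simplest form it divides the as-randomized difference by the engaged fraction, so at 70% engaged the standard error grows by about 1/0.7 = 1.43.
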